## 6.1.2 Secondary study parameters/endpoints (if applicable)

Secondary outcomes are:

- Recurrence at 5 year (identified by record linking[BE] or general practitioner data[NL])
- Recurrences needing surgery
- Recurrence risks stratified by patients and surgical characteristics (Sex, age)
- Recurrence risk in the operative subgroup stratified for laparoscopic vs open surgery
- Morbidity from elective adhesiolysis:
  - Serious adverse events and complications, graded by Clavien-Dindo score.
  - Intra-operative events (i.e. bowel injury), graded by ClassIntra®

- ICU admission
- Reinterventions within 90 days

Patient questionnaires at 1 and 2 years of follow-up

- Health-related quality of life measured by EQ5D
- Gastro-intestinal related quality of life measured by GIQLI
- Characteristics of abdominal pain
- Costs from healthcare perspective (measured by modified iMCQ)
- Costs from societal perspective (measured by modified iMCQ and iPCQ)
- Cost-effectiveness (incremental cost-effectiveness ratio, i.e. cost per QALY) Surgical follow-up
- History taking with focus on potential recurrences
  - Review of data from readmission in same hospital
  - Ask patients if there have been readmission to other hospitals
- Assessment of complaints related to obstruction
  - Chronic or recurrent nausea, bloating, abdominal pain
  - Unintended weight loss
- Physical examination focused on abdominal pain and incisional hernia

The full iMCQ and iPCQ questionnaires are quite extensive and elaborate for patients to fill out. Therefore a modified version of these questionnaires is applied, in which only the domains that are potentially affected by ASBO are included, as decided upon during an expert meeting with healthcare professionals and patient representatives. This method is frequently applied in cost-effectiveness research and also increases the number of patients completing the questionnaire.

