## Surgery

Patient randomized to the intervention will undergo surgery within 6 weeks following inclusion. Surgery will be performed in accordance to the description of the intervention in chapter 5 of the protocol. Peri-operative care will be performed according to local protocols for elective laparoscopic surgery in the operative centres. Based on previous experiences we expected adhesiolysis to be performed laparoscopically in 70-80% of patients. Average hospital stay following laparoscopic adhesiolysis is 2 days. In converted and open surgery cases, the average stay is 5 days. Operatively treated patients will have a single outpatient visit to evaluate the recovery at 6 weeks post- surgery, or more frequent if a complication has occurred (as appropriate in the care for that complication). No specific follow-up is performed after this single post-operative outpatient visit.

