#### Data collection

Follow-up questionnaires will be sent at 6, 12 and 24 months of follow-up. The questionnaire will include surveys of health-related quality of life (EQ5D), abdominal complaints, healthcare costs (iMCQ) and productivity (iPCQ). In addition the questionnaire will cover potential missed episodes of recurrence (e.g. readmission for recurrence when travelling abroad). In case a potential missed episode of recurrence is identified, additional medical information of the readmission is requested to verify if this was an episode of recurrence.

Table 1 provides an overview of the study procedures and moment for data capture. Long-term follow-up

We will perform an extended follow-up of 5 years for the primary outcome of readmission based on data from participating centers and general practitioner data. General practitioner data are important sources for the long-term follow-up as patients
might present at a different hospital with a recurrence of ASBO. In both the Netherlands and Belgium correspondence from all hospital admissions is held by the general practitioner. After review of data from participating hospitals, short questionnaires will be sent to general practitioners to identify potential readmissions for
ASBO outside the group of participating hospitals. We have experience with these
questionnaires in previous studies, and this methods has been shown to accurately
identify readmissions for ASBO. Additional hospital data is requested to verify diagnosis of ASBO in case a potential episode of recurrence is detected through general
practitioner data. Participants will be asked for oral and written consent at inclusion
to contact their general practitioner and other hospitals in the future for long-term follow-up.

In Belgium, general practitioner care is not fully centralized. In case it is difficult to obtain the required information from general practitioners, we will use record linkage to identify potential relevant readmissions using the following procedures by KCE.

After the completion of the study the Sponsor will transfer the pseudonymised study data set to KCE. KCE will request approval from the competent chamber of the Information Security Committee (ISC) to have the relevant study data linked with e.g. IMA data by a trusted third party (TTP, eHealth platform) using the participant national number.

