The Study Data consist of this protocol, including amendments, the electronic forms for data capture, including the annotations and guidance for use, the electronic data-base of the pseudonymized clinical and non-clinical data collected using data capture, including the log of changes from data entry to database lock, study reports based on these pseudonymized data, and any data or reports generated at a later stage, e.g. based on exploratory analyses or stored samples.

"Foreground" means any Study Data, and any tangible biological, chemical and physical material and inventions, that are generated, acquired, discovered, conceived, developed, created, exemplified or derived as a result of carrying out the Clinical Study, whatever its form or nature, whether it can be protected or not, as well as any Foreground IP. Sponsor acknowledges that the main purpose of the research performed under this Agreement is to generate results that will serve the general public interests, and specifically the interests of the patients and public

healthcare decision making bodies, and, therefore, undertakes not to exploit the Foreground in any way that is or could be detrimental to such interests.

The Sponsor owns the Study Data but provides KCE with a copy of the pseudony-mized database after database lock as well as a royalty-free unrestricted license to use the Study Data for non-commercial public health related purposes as detailed in the Agreement between KCE and the sponsor. If judged appropriate, KCE will introduce the request to the competent chamber of the Information Security Committee and arrange for the data linkage. For the sake of clarity, the linked data are not part of the Study Data. However, KCE will discuss with the Sponsor the results of the analyses and the reporting of the linked data.

Table 1 Overview of Study Procedures

	Screening period	Randomisa- tion	Treatment Period 			Midterm follow-up			Long-term follow-up
	Visit 1		Visit 2	Visit 3	Visit 4	Visit 5	Visit 6	Visit 7	
	Max 2 weeks af- ter dis- charge	Max 4 days after visit 1	Day of Surgery (max. 6 weeks after randomisation)	Discharge (~1-7 days after surgery)	Outpatient clinic (2-6 weeks after surgery)	6 months	12 months	24 months	5 years
Informed consent	Х								
Eligibility Assessment	X 	Х							
Randomisation		Х							
Surgical findings			X						
Registration of Physical examination and history taking 	X				X	Х	Х	Х	

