## **Economic evaluation**

Parallel to the clinical trial an economic evaluation will be performed, comparing the costs and effects of elective adhesiolysis and a watch-and-wait policy, in order to determine the most cost-effective approach. The economic evaluation will be performed from a societal and health care payer perspective, adhering to the Dutch and Belgian guidelines respectively.(17,18) The time horizon of the base case analysis of the economic evaluation will be two years. Some of the long-term consequences of aSBO such as chronic pain can continue to cause morbidity and costs beyond the follow-up of the trial. Also new instances of recurrence of aSBO continue to occur at long periods after surgery, beyond clinical trial follow-up. Long-term cost and effects will therefore be evaluated using decision analytical modeling.

Trial-based economic evaluation

The trial-based cost-effectiveness analysis will be conducted with an intention-to-treat

approach and cost-effectiveness is expressed in (incremental) cost per QALY. Costs of the elective surgery will be calculated based on materials needed, operation time and length of hospital stay. Other important health care cost categories are subsequent hospital visits, related adverse events, readmissions, general practitioner, allied health professional visits, and home care services. There may also be patient and family costs, such as out-of-pocket payments, informal care costs and productivity loss. Most health care use is collected as part of the clinical trial. Data on health care use outside of the hospital, informal care and productivity loss are collected the validated iMTA Medical Consumption Questionnaire (iMCQ) and iMTA Productivity Cost Questionnaire (iPCQ), completed by patients at baseline, 6, 12 and 24 months.(19,20) The questionnaires are modified to include those domains that are potentially impacted by ASBO. The Dutch

manual for costing research is used to determine prices for resource use.(21) The EQ-5D-5L survey is used to calculate QALY using area under the curve calculations.(22) The EQ-5D is completed at baseline, 6, 12 and 24 months.

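### EQ-5D at baseline, 6, 12 and 24 months misses recovery from an operation done within 6 weeks, so trial-based QALYs are expected to favour surgery; section 6.1.2 also gives a conflicting schedule

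*Protocol*

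**What the plan says.** - **QALY method (8.2, Economic evaluation).** "The EQ-5D-5L survey is used to calculate QALY using area under the curve calculations". The measurement times follow: "The EQ-5D is completed at baseline, 6, 12 and 24 months". On the horizon: "The time horizon of the base case analysis of the economic evaluation will be two years".
- **Collection schedule (6.3, Data collection).** "Follow-up questionnaires will be sent at 6, 12 and 24 months of follow-up". In the overview of study procedures (Table 1), the quality-of-life row is marked at the screening visit and at 6, 12 and 24 months. It is not marked at surgery, discharge or the post-operative clinic, and those three visits exist only in the intervention arm.
- **Timing of the operation (6.3, Surgery).** "Patient randomized to the intervention will undergo surgery within 6 weeks following inclusion". Table 1 has "max. 6 weeks after randomisation". The same section says "Average hospital stay following laparoscopic adhesiolysis is 2 days"; it gives no time to full recovery at home.
- **A different schedule (6.1.2).** The EQ-5D, the GIQLI, abdominal pain, the cost measures and cost-effectiveness are listed under "Patient questionnaires at 1 and 2 years of follow-up".
- **Use of the result.** Cost per QALY is a listed secondary outcome. Section 8.2 plans an ICER, a bootstrap and an acceptability curve, and costs the operation from materials, theatre time and length of stay. Scenario and one-way sensitivity analyses are announced without detail, and none is described as an operative utility decrement.

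**The concern.** The baseline EQ-5D is taken before randomisation and the next one at month 6. The operation and the convalescence both lie between them. A straight line from pre-operative health to health at month 6 passes over any loss that has resolved by then. Short episodes of recurrence can be missed in the same way, but they are scattered over two years and differ little in number between arms. The operation comes early and in nearly every patient of one arm, so the two omissions do not balance.

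What is at stake is the effect side of the trial-based ICER: the hospital costs of surgery enter the calculation and its short-term health cost does not. Bootstrapping resamples the same measured points and cannot show the gap. Early utilities that were never collected cannot be recovered by a later analysis plan. Separately, section 6.1.2 leaves it unclear whether the 6-month questionnaire is part of the outcome set.

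**Working it through.** The protocol states no QALY figure to reproduce. Inputs from the protocol: EQ-5D at weeks 0, 26, 52 and 104; surgery by week 6; two-year recurrence of 20% and 10% (4.4). Assumptions: months count from randomisation, points are joined by straight lines, and the EQ-5D reflects health when it is completed. The protocol gives no utilities, so the drops and durations below are also assumed.

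**1. The gap.** 26 − 6 = 20 weeks at least between surgery and the next EQ-5D. A recovery complete within 20 weeks falls wholly inside it.

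**2. Loss per operated patient, constant drop d for r weeks.** L = d × r / 52.

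| d | r (weeks) | True loss (QALY) | Recorded at 0/6/12/24 months | Recorded at 0/12/24 months |
|---|---|---|---|---|
| 0.1 | 2 | 0.004 | 0 | 0 |
| 0.2 | 4 | 0.015 | 0 | 0 |
| 0.3 | 6 | 0.035 | 0 | 0 |

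If health recovers linearly instead of all at once, each loss halves (0.002, 0.008, 0.017) and the recorded loss is still 0.

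**3. Recurrences.** The trapezoid weights are 13, 26, 39 and 26 weeks (sum 104). The three follow-up points carry 26 + 39 + 26 = 91 weeks, so an episode at a uniformly random time is captured on average at 91/104 = 87.5%. It is missed in most patients and over-weighted in a few. The arms differ by 0.20 − 0.10 = 0.10 recurrences per patient.
- If all intervention patients are operated on and 12.5% of the recurrence loss is unseen, a recurrence must cost 1 / (0.10 × 0.125) = 80 times an operation to cancel the missed operative loss.
- If every recurrence is unseen, the ratio is 1 / 0.10 = 10.
- If, in addition, all 20% of controls recur, cross over and have that operation missed, it is (1 − 0.20) / 0.10 = 8.

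Patients who decline surgery lower these ratios in proportion.

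**4. Scale.** With linear recovery, a recurrence costing 0.2 over 2 weeks to 0.5 over 8 weeks loses 0.2 × 2 / 2 / 52 = 0.004 to 0.5 × 8 / 2 / 52 = 0.038 QALY. Times 0.10, averted acute episodes are worth about 0.0004 to 0.004 QALY per patient, not counting chronic complaints or mortality. The linear-recovery operative loss in step 2 is 0.002 to 0.017.

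**5. Early lasting gain.** Suppose surgery is at week s and utility settles at g above baseline after recovery. Up to week 26 the patient truly has g for 26 − s − r weeks, and the straight line credits 13. Net error in favour of surgery = [d × r − g × (13 − s − r)] / 52. With s = 4 and g = 0.05:
- d = 0.1, r = 2: (0.2 − 0.35) / 52 = −0.003, so against surgery. The sign changes at g = 0.2 / 7 = 0.029.
- d = 0.2, r = 4: (0.8 − 0.25) / 52 = +0.011. The sign changes at g = 0.8 / 5 = 0.16.
- d = 0.3, r = 6: (1.8 − 0.15) / 52 = +0.032. The sign changes at g = 1.8 / 3 = 0.6.

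**6. Which early times would work.** Take surgery dates uniform over weeks 0 to 6 and a 4-week loss of 0.2 (true 0.0154).
- Added at weeks 8 and 13: week 8 has weight 4 + 2.5 = 6.5. Surgery in week 2 records 0; surgery in week 6 records 0.2 × 6.5 / 52 = 0.025. Only dates in weeks 4 to 6 (one third) are seen, so the average is 0.025 / 3 = 0.0083, or 54% of the truth.
- Added at weeks 4, 8 and 13: weights at weeks 4 and 8 are 4 and 4.5. Dates in weeks 0 to 4 are seen at week 4 and dates in weeks 4 to 6 at week 8. The average is 0.2 × (4 × 2/3 + 4.5 × 1/3) / 52 = 0.0160, or 104%. The same calculation gives 67% for a 2-week loss (4 × 1/3 = 1.33 of 2 weeks) and 94% for a 6-week loss (4 × 2/3 + 4.5 × 2/3 = 5.67 of 6 weeks).

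**The case against.** A reader might infer that the schedule always favours surgery. The protocol does not support that. Section 9.4 expects that adhesiolysis may relieve chronic complaints, and step 5 shows that such a gain, arriving early, is under-credited; with a small, short post-operative drop it reverses the sign. A complication that persists to month 6 would be recorded, and could even be over-weighted. This objection stands, and it limits the claim to an expected direction.

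Nor can the net bias be written as a fixed fraction of the operative loss, such as one minus the difference in recurrence. That would treat every recurrence as unseen and every allocated patient as operated on, and would equate an elective operation with a recurrence. Section 6.6 provides for patients who refrain from surgery, section 6.3 allows cross-over after recurrence, and randomly timed recurrences are largely captured on average.

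It is also fair that the protocol leaves room for scenario analyses, that the decision model may take inputs from outside the trial, and that the sponsor deliberately shortened the cost questionnaires to help completion. An analysis plan not seen here may name an operative decrement. It could not supply early EQ-5D data that were never collected.

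Finally, 6.1.2 should not be read as showing that the 6-month questionnaire is dropped: 6.3, Table 1 and 8.2 all include it, so 6.1.2 is most likely a slip.

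**Conclusion.** The point holds as a limited, inexpensive improvement. A post-operative loss that resolves before month 6 contributes nothing to the trial-based QALYs, and the expected net error favours surgery. The direction rests on most allocated patients being operated on, on the 10-percentage-point difference in recurrence, and on no early lasting gain large enough to offset the loss. The missed amount, about 0.004 to 0.035 QALY per operated patient for a constant drop, rests entirely on assumed utilities. The documents cannot show that it would change the cost-effectiveness conclusion. The effect is confined to the trial-based QALYs and ICER, and to the decision model if it draws its early utilities from the trial. The contradiction between 6.1.2 and the other three places is plain and does not depend on any assumption.

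**What to change.** 1. Send the EQ-5D alone, without the cost questionnaires, to both arms at the same early times after randomisation. Space them to cover surgery dates from week 0 to week 6, for example about 4 weeks, 8 weeks and 3 months. Use the existing questionnaire route, not visits 2 to 4, which exist in one arm only. Add the times to 6.3, Table 1 and 8.2. Eight weeks and 3 months alone would catch only about half of a 4-week loss.
2. If no collection can be added, prespecify a sensitivity analysis, not the base case, that applies an operative utility decrement over a stated range to every adhesiolysis in either arm, including cross-overs. Do not add a decrement for recurrences, which the EQ-5D already largely captures on average; that would count them twice.
3. Correct the questionnaire times in 6.1.2 to agree with 6.3, Table 1 and 8.2.

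The cost is a small amendment and three short forms per patient, with slight added burden. Items 2 and 3 need no new data.

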#### Model-based economic evaluation

We evaluate the 5-year and lifetime cost per QALY by developing a de novo decision-analytic model. We use the Dutch societal perspective, and the Belgian perspective will be explored. The ZIN guideline for economic evaluations in healthcare will be followed, for example including productivity losses using the friction cost approach.(21)The conceptual model will be developed based on a review of existing cost-effectiveness models and interviews with clinical and patient experts. It will likely be a state transition model, which means that patients can transit through different relevant health states through their lifetime. Data inputs are informed based on trial data and, where not available from the trial, identified through targeted reviews, expert interviews, hospital records, and data linkage. Long-term data on risk of recurrence will be extrapolated from the trial using survival analysis. The model will be developed in MS excel. Validation efforts include technical verification using the TECH-VER checklist, as well as expert interviews.(25) We explore uncertainty through (probabilistic) sensitivity and scenario analyses.

#### 8.3 Other study parameters

Baseline parameters will be compared by independent samples t-test for continues outcomes and chi-square for dichotomous outcomes.

## 8.4 Interim analysis (if applicable)

An Interim analysis measuring safety outcomes is planned after 140 and 280 patients are included. In this interim analysis, we will primarily evaluate adverse events related to the intervention. Most patients will not have completed follow-up at the interim analysis, and therefore no futility analysis is performed. A data safety monitoring board will be installed to keep an overview of the (severe) adverse events and decide whether the study will be terminated when patients are at an increased risk of developing grade 3b or higher adverse events with prolonged negative impact on patients health.

Version number: 2, 25-04-2025 32 of 44

#### 9. ETHICAL CONSIDERATIONS

## 9.1 Regulation statement

The study will be conducted according to the principles of the Declaration of Helsinki (version October 2013), in accordance with the Medical Research Involving Human Subjects Act (WMO) and applicable local regulations of the participating countries as well as other European guidelines, regulations and acts such as the GDPR (General Data Protection Regulation, in Dutch: Uitvoeringswet AVG).

#### 9.2 Recruitment and consent

Patients are identified by their treating physician or surgeon during admission for aSBO. Patients in whom aSBO resolves with conservative treatment are eligible.

The treating surgeon or physician will discuss the option of participating in the study and give a short introduction on what participation entails at discharge.

The treating physician will verbally ask permission to the patient for the study team to contact the patient and inform further about the trial and schedule an outpatient visit at an operative centre to provide full information on the trial and discuss participation, non-committal. Patients referred to discuss participation in the trial will receive written information about the trial at a minimum of 5 days prior to the outpatient clinic meeting. The outpatient clinic meeting will be scheduled within two weeks from discharge when the patient has fully recovered. Patients who agree to participate in the study will provide written informed consent to participate in the study. Patients remain free to withdraw at will at any time from the study without giving a reason.

Eligible patients that agree to receive detailed information to consider participation will receive the Patient Information Form (PIF), the Informed Consent (IC) form and the patient information brochure from the study team online via e-mail prior (at a minimum of 5 days prior to the outpatient clinic meeting) to the visit to the outpatient clinic. The PIF explains the rationale behind the study, as well as what participation entails. An outpatient clinic appointment at an operative centre is scheduled within two weeks from discharge. During the outpatient clinic meeting, eligibility of the patients will be further assessed by a surgeon and anesthesiologist. The surgeon will also discuss in detail the intervention in the study as well as the prognosis of watchful waiting, and provides a possibility for further questions on the intervention. If patients require more time for a decision about participation a digital follow-up visit is scheduled at 4-5 days. If the patient decides to participate informed consent will be signed digitally or on paper at the outpatient visit, or a digital follow-up visit, by the patient and a representative of the study team.

Version number: 2, 25-04-2025 33 of 44

The intervention will be scheduled at the operative center where the patient has visit the outpatient clinic.

**9.3** Objection by minors or incapacitated subjects (if applicable) Not applicable.

Version number: 2, 25-04-2025 34 of 44

